9 CLINICAL SITE MONITORING

The Research Project Coordinators (RPCs) and the Research Exercise Trainer (RET) (under the direction of the Co-PIs [name] and [name]) will conduct audits to monitor compliance with intervention and testing protocols and to monitor unanticipated problems involving risks to the subjects at random times and at least every 3 months of the study. Reports of violations will be submitted to the IRB as required. The conduct and scientific integrity of this proposed clinical trial will also be monitored by a Data and Safety Monitoring Committee (DSMC). The DSMC will audit the implementation of the protocol beginning 6 months after the start of subject accrual. Since this trial is greater than minimal risk, it will be audited every 6 months. Each report will include monitoring of: compliance with informed consent and eligibility requirements, recruitment plan according to protocol, follow-up data collection according to protocol, expected and actual accrual, protocol violations, and patient withdrawals from the study. Per university policy, all serious adverse events (AE) will be reported to the UNMC IRB, the NIH, and to the DSM Committee within two business days after the investigators have been notified of the AE. The investigators will prepare a summarized report of these above-listed items and submit this report to the DSMC, with access to raw data if needed. A report from the DSMC audit will be sent to the investigators, the UNMC IRB, and NINR-NIH.

The same auditing plan will be used for external study sites involved in the study, including all "Y" facilities and the Creighton University Research Center. As described previously, audits will be conducted by the RPCs and RET (under the direction of the Co-PIs [name] and [name]) and also by the DSMC.

10 DATA ENTRY/STATISTICAL CONSIDERATIONS

10.1 Data Entry

As indicated in Section 9.1.1, HOPS data will be entered and stored on a password protected, secured campus UNMC RedCAP database server. The server is accessible from an external network, therefore the database offers the capability to enter data off site. We will be utilizing Ipads to enter participant data offsite, and data will be entered by both HOPS personnel and participants. Styluses and keyboards have been purchased to increase ease of entry and to minimize error. Additionally, limitations have been set in RedCAP so that the database will notify the user any time a value outside of the normal range is submitted, allowing the user an opportunity to correct an error. In order to avoid any risk of violations of confidentiality, participants will have limited access to RedCAP, and will therefore, only be able to view the necessary forms.

See [Protocol 24. RedCap Data Entry](#) for detailed directions on data entry and usage of the RedCAP database.

10.2 Sample Size Considerations

A power analysis was conducted for the primary aim of the study since it involves the most complex analysis. Hypothesis 1a states that at 12 months, there will be significantly greater improvements in BSI at the 4% tibial site in subjects in the exercise group compared to subjects in the control or risedronate groups. Power for the repeated measures analysis of variance (RM-ANOVA) was determined using G*Power3.1.5. A within-between interaction will be the primary test of significance (time*group interaction). It is assumed that the exercise group will have significantly greater improvements in BSI than either the control or risedronate groups. Two groups were assumed for the purposes of the power analysis because the control and risedronate groups will be compared to the exercise group separately. The total sample size will then be the number determined plus one half to populate the three groups. We investigated effect size evidence from similar studies and a variety of effect sizes was observed. However, effect sizes were not reported in the studies that were deemed most similar to the planned study. This study compares an exercise group to control and risedronate groups, which is unique so a large expected effect size could not be assumed without further evidence. Therefore, a small effect size was assumed for this power analysis ($f=.10$; Cohen 1992). Assuming a significance level of .05, 3 time points, and an estimate of .5 for the correlation between time points, 246 participants (82 per group) would be needed to have 80% power.

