Description of Intervention:	
This proposed study has a randomized 3-group (2 treatment groups & 1 control group), repeated measures experimental design. A computer generated code will be used to stratify subjects by exercise at baseline and then randomized to 3 groups (Control: n =103; Risedronate: n =103; Exercise: n =103) with assignments placed in sealed opaque envelopes for sequential use. All subjects will take dosages of calcium citrate supplements sufficient to ensure their total daily calcium (diet+supplements) is ~ 1200 mg daily and vitamin D³ supplements with daily dose to ensure serum levels of vitamin D [25 (OH)D] are between 30 ng/mL and 80 ng/mL(optimal CaD). Subjects randomized to the Risedronate group will take optimal CaD daily and 150mg of oral risedronate once monthly for 12 months but will not participate in the exercise program. Subjects randomized to the Exercise group will take optimal CaD and also participate in 12 months of a bone-loading exercise program three times weekly at a local community-based YMCA (Y). To ensure the bone outcomes were not due to the CaD supplementation, a group taking only optimal CaD will serve as a control. While only women in the exercise group will participate in the structured bone-loading exercise program developed for this study, all women will be encouraged to participate in exercises and will be informed of the benefit of weight bearing and resistance exercises. The primary outcome will be bone structure at the tibia and hip and secondary outcomes are bone mineral density (BMD) and bone turnover. Repeated measures of primary and secondary outcome variables will be conducted at baseline, 6 and 12 months to better understand response to intervention components with a

	maximum difference expected at 12 months. An exercise intervention lasting 12 months or 2 to 3 bone turnover (resorption / formation) cycles is necessary in order to measure the effects of training on bone outcomes.
Study Duration:	Time from subject enrollment to completion of analysis is 4 years and 6 months.
Subject Participation Duration:	Each subject will be asked to participate in the study for a total of 12 months.
Estimated Time to Complete Enrollment:	Study enrollment will begin in Year 1, month 6 and continue through Year 4, month 9.

SCHEMATIC OF STUDY DESIGN:

See [Protocol 1. Timeline for Data Collection](#), for details regarding collection of specific measures

Prior to
Enrollment

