3 OBJECTIVES

3.1 *Study Objectives*

Our **long-term goal** is to contribute to the development of clinical practice guidelines for the promotion of bone health in postmenopausal women with low bone mass. Our **central hypothesis** is that improvements in bone health will be greater in subjects randomized to the Exercise group compared to subjects in either the Control or Risedronate groups.

Aim1: To compare Control, Risedronate, and Exercise group subjects on changes in bone structure at the tibia (bone strength index [BSI]: pQCT) and hip (femoral neck and shaft, intertrochanteric) (hipstructural analysis: [HSA: DXA]) at baseline, 6, 12 months.

H1a: At 12 months, there will be significantly greater improvements in bone strength index (BSI) at the 4% tibial site in Exercise subjects compared to subjects in either Risedronate or Control groups

H1b: At 12 months, there will be significantly greater improvements in bone mass distribution (HSA; centroid, mm) at the femoral neck in Exercise subjects compared to subjects in either Risedronate or Control groups

Aim2. To compare Control, Risedronate, and Exercise group subjects on changes in BMD at the total hip, femoral neck, and spine (DXA) at baseline, 6, and 12 months.

H2a: At 12 months, there will be significantly greater improvements in BMD at the total hip, femoral neck, and spine in Exercise and Risedronate subjects compared to subjects in the Control group

H2b: At least 80% of subjects in both the Exercise and Risedronate groups will have preserved BMD at the total hip, femoral neck, and spine.

Aim3: To compare Control, Risedronate, and Exercise group subjects on changes in bone formation and resorption at baseline, 6, 12 months. (formation: AlkphaseB, resorption: Serum NTx).

H3a: At 12 months there will be significantly greater decreases in serum markers of bone resorption (Serum NTx) in subjects in the Exercise and Risedronate groups compared to subjects in the Control group

H3b: At 12 months, mean Serum NTx levels for subjects in both Exercise and Risedronate groups will have decreased to levels considered at low risk for fracture (< 12.6 nmol BCE/L)

H3c: At 12 months, there will be significantly greater improvements in serum markers of bone formation (Alkphase B) in Exercise subjects compared to subjects in either Control or Risedronate group subjects

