4 STUDY DESIGN

This study has a stratified, randomized 3-group (2 treatment groups & 1 control group), repeated measures experimental design. A computer generated code will be used for randomization to 3 groups (Control: n =103; Risedronate: n =103; Exercise: n =103) with assignments placed in sealed opaque envelopes for sequential use. All subjects will take dosages of calcium citrate supplements sufficient to ensure their total daily calcium (diet+supplements) is ~ 1200 mg daily and vitamin D³ supplements with daily dose to ensure serum levels of vitamin D [25 (OH)D] are between 30 ng/mL and 80 ng/mL(optimal CaD). Subjects randomized to the Risedronate group will take optimal CaD daily and 150mg of oral risedronate once monthly for 12 months but will not participate in the exercise program. Subjects randomized to the Exercise group will take optimal CaD and also participate in 12 months of a bone-loading exercise program three times weekly at a local community-based Y. To ensure the bone outcomes were not due to the CaD supplementation, a group taking only optimal CaD will serve as a control. We believe it would be unethical for women at risk for further bone loss to have restrictions in physical activity for 12 months. Thus, while only women in the exercise group will participate in the structured bone-loading exercise program developed for this study, all women will be encouraged to participate in exercises and will be informed of the benefit of weight bearing and resistance exercises. **The primary outcome will be bone structure at the tibia and hip and secondary outcomes are BMD and bone turnover.** Repeated measures of primary and secondary outcome variables will be conducted at baseline, 6 and 12 months to better understand response to intervention components with a maximum difference expected at 12 months. An exercise intervention lasting 12 months or 2 to 3 bone turnover (resorption / formation) cycles is necessary in order to measure the effects of training on bone outcome

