10.3 Final Analysis Plan

Aim 1 hypotheses will be tested via RM-ANOVA models. Bone strength index at the tibia and bone mass distribution at the hip, the dependent variables of interest, will be measured at 6-month intervals (0, 6, and 12 months). A significant time*group interaction would indicate that the two groups being compared in each model have significantly different changes in bone structure over 12 months. Huynh-Feldt corrected F-tests will be used in order to account for any possible violation of sphericity. It is hypothesized that the exercise group will have significantly greater improvements than the control or risedronate groups. Up to 20% attrition may be expected over the course of the study, but we expect it

to be less due to the use of cognitive behavioral strategies by Research Project Coordinators (RPC), the Research Exercise Trainer (RET), and ETs to promote exercise adherence and retention in the study. The method of handling missing data is not likely to have an effect with small amounts of missing data. However, If there is a higher than expected attrition rate, a maximum likelihood estimation method (e.g. mixed models) will be used instead of RM-ANOVA in order to utilize all available data and not delete cases in a listwise manner.

Hypothesis 2a compares the groups changes in BMD and will also be analyzed using RM-ANOVA. Hypothesis 2b also involves BMD, but assesses the proportions of preservation of BMD in each group. It is expected that at least 80% of subjects in both the exercise+ and risedronate+ groups will have preserved BMD at the three skeletal sites, and that the control/CaD group will have a significantly lower proportion of participants preserving BMD over 12 months. In order to classify individuals into preserved vs. declined groups, change in BMD over 12 months will be compared to the least significant difference as defined by the Hologic DXA manufacturer for each respective skeletal site. Differences of proportion of preservation across groups will be assessed via chi-square tests, which would indicate if preservation of BMD was significantly different across groups. Aim 3 investigates the changes in bone formation and resorption over 12 months also using repeated-measures ANOVA. Alkphase B and Serum NTx will be measured at baseline, 6, and 12 months.

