The relationships of interest in Aim 4 will be explored by assessing the correlations between percentage of sessions attended, percentage of risedronate pills taken, and 12-month changes in bone structure at the tibia and hip. Assuming the variables are normally distributed, Pearson correlations will be used. Spearman rank correlations will be used if any of the variables are found to be non-normal.

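### The primary test is a two-degree-of-freedom time-by-group interaction that does not isolate the 12-month difference claimed in H1a and H1b, and no 12-month contrast, estimate or confidence interval is planned for them

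*Combined protocol and SAP*

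**What the plan says.** Section 3.1 states both primary hypotheses as directional claims about one visit. For the tibia: "H1a: At 12 months, there will be significantly greater improvements in bone strength index (BSI) at the 4% tibial site in Exercise subjects" against either comparator. For the hip: "H1b: At 12 months, there will be significantly greater improvements in bone mass distribution (HSA; centroid, mm) at the femoral neck in Exercise subjects", again against either comparator. H2a, H3a and H3c have the same form. Section 4 explains the repeated visits as a way "to better understand response to intervention components with a maximum difference expected at 12 months".

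Section 10.2 restates H1a and then names the test: "A within-between interaction will be the primary test of significance (time*group interaction". It sizes the trial on that test for two groups at a time. Section 10.3 analyses Aim 1 by two-group RM-ANOVA over 0, 6 and 12 months with Huynh-Feldt corrected F-tests, and interprets the result this way: "A significant time*group interaction would indicate that the two groups being compared in each model have significantly different changes in bone structure" over the 12 months.

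Nothing for H1a or H1b follows that test. The mixed-model fallback for high attrition names no 12-month contrast either. Two other analyses do look at 12 months: the H2b proportions with preserved BMD, and the Aim 4 correlations, which use "12-month changes in bone structure at the tibia and hip". Neither tests H1a or H1b.

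On the design side, the Protocol Summary (Description of Intervention) says: "A computer generated code will be used to stratify subjects by exercise at baseline and then randomized to 3 groups". Section 10.3 does not include that stratum in any model.

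**The concern.** The hypothesis and the test ask different questions. The hypothesis is about one visit and one direction. The interaction asks whether the two mean profiles differ in shape anywhere across three visits, in either direction. A 12-month difference does drive it, but so does a difference confined to 6 months, or Exercise doing worse.

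After a significant result, the team would still need a further analysis to say who did better, by how much and whether it holds at 12 months. Because that analysis is not written down, its form would be open to choice after the data are seen. A trial meant to inform practice guidelines also needs an effect estimate with an interval, and the primary analysis names none.

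Three things are not in dispute. Baseline enters as the first repeated measure, so the planned test does compare changes from baseline. Its type I error holds. Using baseline as a covariate instead is a matter of efficiency, not a correction for bias.

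**Working it through.** **Inputs.** From section 10.2: f = .10, alpha .05, m = 3 time points, correlation rho = .5, two groups per model, 82 per group (N = 164 per model), 80% power. The documents give no SD, no target 12-month difference and no time profile. The profiles and the other rho values below are therefore assumptions. Equal variances and equal correlations between visits are assumed throughout.

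**1. The plan's own figure.** Degrees of freedom are (2−1)(3−1) = 2 and 2(N−2) = 324. The noncentrality is f²·N·m/(1−rho) = 0.01 × 164 × 3 / 0.5 = 9.84. Noncentral-F power is 80.5%; with N = 162 it is 79.98%. Then 164 × 1.5 = 246, exactly as stated. This confirms that the trial was sized for the 2-df interaction.

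**2. What f = .10 means at 12 months.** With d_t the between-group difference at visit t in SD units, f² is the mean over visits of ((d_t − d̄)/2)². For a 12-month difference D:
- linear profile (0, D/2, D): D = f·√24 = 0.490 SD;
- late-only (0, 0, D) or complete by 6 months (0, D, D): D = f·√18 = 0.424 SD.

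**3. Power of a two-sided 12-month contrast, 82 per arm.** Noncentral t with noncentrality D/(s·√(2/82)). For the baseline-adjusted contrast, s = √(1−rho²) = 0.866 with 161 df. For the unadjusted change score, s = √(2(1−rho)) = 1.0 with 162 df.

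| Profile | 12-month difference | Interaction | Baseline-adjusted | Change score |
|---|---|---|---|---|
| Linear | 0.49 SD | 80.5% | 95.0% | 87.7% |
| Late-only or complete by 6 months | 0.42 SD | 80.5% | 87.7% | 77.1% |

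The adjusted contrast reaches 80% power with 51 per arm (linear) or 67 per arm (the other two profiles).

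**4. Sensitivity to rho** (N = 164).

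| Assumed rho | f | Interaction | Adjusted, linear | Adjusted, late-only or by 6 months |
|---|---|---|---|---|
| .7 | .0775 (reset to hold 80.5%) | 80.5% | 92.3% | 83.4% |
| .9 | .0447 (reset to hold 80.5%) | 80.5% | 89.2% | 79.1% |
| .7 | .10 (kept) | 95.9% | 99.2% | 96.6% |

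With f reset, the gain is +3 to +12 points at rho = .7 and −1 to +9 at rho = .9. With f = .10 kept at rho = .7, it is +0.6 to +3.3.

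**5. Does a significant interaction establish a 12-month difference?** Simulation at 82 per arm and rho = .5, at least 10,000 trials per profile:
- 0.42 SD at 6 months, none at 12: interaction significant in 80%, adjusted 12-month contrast in 5%.
- 0.42 SD at 6 months fading to 0.21 at 12: 67% against 34%. About 59% of those significant interactions have no significant adjusted 12-month difference.
- Exercise worse by 0.49 SD at 12 months on a linear profile: interaction significant in about 80%, the same as when Exercise is better.

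**6. Type I error.** The simulated rate for the planned test was 5.0% under the null. It was 5.0% and 4.8% when a time-constant stratum explained 5% and 10% of variance. Omitting the stratum therefore causes no type I error problem.

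**The case against.** The strongest reply is that the striking figures in step 5 need an effect that peaks at 6 months, whereas the plan expects the largest difference at 12. Under the profiles the plan does expect, the interaction rarely misleads. At rho = .5, among significant interactions, the adjusted 12-month difference is significant and favours Exercise in 99% (linear), 96% (late-only) and 93% (complete by 6 months). That stands. The 6-month-peak cases are logical possibilities, not forecasts.

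Second, much of the power gain comes from the baseline covariate rather than from focusing on 12 months. An unadjusted change contrast ranges from about 3 points worse than the interaction to 7 points better. The gain also depends on rho, which the plan gives only as an estimate. Both points stand, so the power argument is secondary.

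Third, reported group means would show direction, and a two-sided test of a directional hypothesis is ordinary. This is partly right, since the proposed contrast is two-sided as well. But inspecting means is not a pre-specified estimate or interval, and does not establish that the difference is present at 12 months.

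Finally, adding one sentence to section 10.3 that commits to a 12-month difference with its interval would close much of the gap. It would, but the declared primary test would still not be the test of the declared hypothesis.

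**Conclusion.** The concern holds for H1a and H1b: the primary test does not isolate the 12-month difference they predict, and no contrast, estimate or interval is specified to do so. It is a mismatch between hypothesis and test. It is not an error in the sample size, the type I error or the stated power. It should be fixed, but it does not invalidate the design.

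At rho = .5, replacing the interaction with a baseline-adjusted 12-month contrast raises power from 80.5% to between 87.7% and 95.0%, depending on the time profile. At an assumed rho of .9, with f reset to hold the interaction at 80.5%, the change is between −1 and +9 points. The case for changing the test rests mainly on answering the stated question directly, and this does not depend on those assumptions.

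**What to change.** - In sections 10.2 and 10.3, make the primary test for H1a and H1b the 12-month Exercise-minus-comparator contrast, reported as an estimate with a 95% confidence interval. Take it from an ANCOVA or mixed model with the baseline value as covariate.
- Keep the time-by-group interaction as a supportive description of the time course.
- Use the same form for H2a, H3a and H3c, with the comparisons that each one names.
- Restate the power basis in section 10.2 as a 12-month difference: 0.42 to 0.49 SD at rho = .5, depending on the assumed profile.
- Include the baseline-exercise stratum as a covariate, because the randomisation used it. The reason is consistency with the design; no gain in error control is claimed.

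**Cost.** No new data and no more participants, only revised wording in 10.3 and a restated sample-size paragraph in 10.2. There are two downsides. The primary test would no longer respond to an effect present only at 6 months. And if rho is near .9 with an effect that is complete by 6 months or appears only afterwards, power is about 1 point below that of the interaction.

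### The 80% power stated for H1a is for one Exercise comparison; power to beat both comparators is about 64–69% at 82 per group, and section 10.3 does not say whether both are required

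*Combined protocol and SAP*

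**What the plan says.** Section 3.1 states the central hypothesis as follows: "improvements in bone health will be greater in subjects randomized to the Exercise group compared to subjects in either the Control or Risedronate groups". H1a expects greater 12-month gains "in bone strength index (BSI) at the 4% tibial site in Exercise subjects compared to subjects in either Risedronate or Control groups". H1b has the same structure for the hip: "H1b: At 12 months, there will be significantly greater improvements in bone mass distribution (HSA; centroid, mm) at the femoral neck", again with Exercise against the other two arms.

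Section 10.2 powers the trial on H1a through the time*group interaction of a repeated measures ANOVA. Two groups are assumed because "the control and risedronate groups will be compared to the exercise group separately", and the result is increased by one half to fill the third arm. The inputs and result are: "Assuming a significance level of .05, 3 time points, and an estimate of .5 for the correlation between time points, 246 participants", which is 82 in each arm, for 80% power with f=.10. That effect size is a conventional small value, used because "effect sizes were not reported in the studies that were deemed most similar to the planned study".

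Section 10.3 says a significant interaction shows that "the two groups being compared in each model have significantly different changes in bone structure over 12 months". It continues: "It is hypothesized that the exercise group will have significantly greater improvements than the control or risedronate groups". It gives no rule for putting the two models together, no testing order and no adjustment. The only significance level is the .05 in section 10.2.

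**The concern.** The hypothesis names two comparators, while the power figure covers one. Beating calcium and vitamin D alone, and beating the drug as well, support different conclusions about trying exercise before bisphosphonates. The plan should therefore fix in advance which result meets H1a.

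Either reading leaves a gap. If both comparisons must be significant, the 80% attached to H1a is not the power to meet it. If one is enough, two unadjusted tests at .05 do not hold the 5% level. Without a written rule, a split result could be called a success or a failure after the data are seen.

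**Working it through.** **Inputs.** From section 10.2: alpha .05, f=.10, m=3 time points, rho=.5, k=2 groups per test, 82 completers per group. From the Protocol Summary: equal allocation, 309 recruited (103 per group). My assumption: f=.10 holds for Exercise against each comparator.

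**1. The plan's own figure.** For a within-between interaction, lambda = f² × N × m / (1 − rho), with df1 = (k − 1)(m − 1) and df2 = (N − k)(m − 1).
- N=164: lambda = 0.01 × 164 × 3 / 0.5 = 9.84; df1 = 2; df2 = 162 × 2 = 324; power 0.805.
- N=162: power 0.7998, just short.
- 164 × 1.5 = 246, or 82 per group, an exact match.
- A three-group omnibus test would need 204.

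So the 80% belongs to one pairwise test.

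**2. Both comparisons.** The two tests share the Exercise arm, so they are positively correlated and the joint power cannot be read off the formula. I simulated three-arm trials with 82 per arm (400,000 per setting), with Control and Risedronate on the same trajectory.

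| Outcome on H1a | Probability |
|---|---|
| A given comparison significant | 0.805 |
| Both significant | 0.692 |
| At least one significant | 0.918 |
| Exactly one significant | 0.226 |

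These agree with each other: 0.805 + 0.805 − 0.692 = 0.918, and 0.918 − 0.692 = 0.226. A separate raw-data simulation (20,000 trials) gave 0.695 for both.

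**3. Different time patterns in the two comparators.** With three visits the interaction effect has two dimensions, so f=.10 can hold against both comparators with differently shaped differences. At angles of 30, 60 and 90 degrees between the two effect profiles, power for both is 0.683, 0.664 and 0.645. Treating the tests as independent gives 0.805² = 0.648. Hence the range 64–69%, with 69% the favourable end.

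**4. More completers (same trajectory).** Power for both is 0.764 at 93 per group, 0.802 at 100 and 0.817 at 103.

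**5. Other inputs (assumed, 82 per group, same-shaped effects).** Power for both is 0.585 at rho=.4 and 0.814 at rho=.6. It is 0.772 with f=.10 against Risedronate and .12 against Control, and 0.539 with .08 and .10.

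**6. Error rates with no true difference (1,000,000 trials).** The interaction F-test has no direction, so results favouring Exercise are shown separately.

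| Rule for H1a | Any direction | Favouring Exercise |
|---|---|---|
| One test at .05 | 0.050 | 0.025 |
| Either of two, unadjusted | 0.092 | 0.046 |
| Either of two, Holm | 0.047 | 0.024 |

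If both tests are required, the null rate is 0.009. If Exercise truly beats one comparator but not the other, the false H1a rate cannot exceed the 5% of the remaining test.

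**7. Power under Holm across the two.** 0.770 per comparison and 0.682 for both (same trajectory).

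**The case against.** The strongest reply is that section 10.2 hides nothing. It says it assumed two groups and why, and it never claims joint power. That stands: 246 is correct for what it describes. A reader might infer that the sample size is miscalculated or that more women must be recruited; the documents support neither.

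Second, the either/or wording most naturally means better than each comparator. That also stands. A reader might infer that the plan tests at 9% rather than 5%, but that figure applies only if one win is enough. Under the natural reading the H1a error rate is controlled and the problem is power alone. The wording still leaves some room, and section 10.3, reading model by model, does not close it.

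Third, 82 per group is the case at full planned attrition. Section 10.3 expects less than 20%, and section 5.4.2 keeps off-protocol subjects in testing. With 93 to 103 completers, joint power is 76–82%, so the shortfall may shrink or vanish. But 103 means no dropout at all, and 82 is the number the plan itself is built on.

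Fourth, if each comparison is its own hypothesis, 80% is the relevant power, and adjusting across distinct comparators is debated. This is a legitimate choice, but the plan does not state it.

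Finally, a flat 69% would be too firm. It needs equal effects against both comparators and a shared trajectory, neither of which the documents establish.

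**Conclusion.** Wrong as written: the power stated for H1a is not the power to meet H1a against both comparators. At 82 completers per group, with rho=.5 and f=.10 against each, that power is about 64–69%, some 11 to 16 points below the stated 80%. If one win is enough, power is about 92%, but the unadjusted error rate is about 9% (4.6% favouring Exercise, against 2.5% for one test). Under the same-trajectory case, about 23% of trials would end with exactly one significant comparison, and the plan does not say how to read that.

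The result depends on f=.10 holding against both comparators. Because that is a conventional value, the joint figure is a planning figure and not a forecast.

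A reader might also want to extend the point to all four H1a and H1b tests. The plan is silent on alpha there too, but this is secondary. The null chance of at least one significant result in four is about 15–18% for an assumed endpoint correlation of 0.7 down to 0. Power would further need an assumed H1b effect. The documents give neither input, so such numbers should not be printed as protocol figures.

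**What to change.** **Section 10.2.** State that the 80% is per comparison. Add that power to beat both comparators on H1a is about 64–69% at 82 completers per group under the plan's inputs, assuming f=.10 against both.

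**Section 10.3.** State that the H1a claim requires both comparisons to be significant at .05, with no alpha split. If the sponsor instead wants a separate claim for each comparator, use Holm across the two at a family-wise .05; this gives about 77% per comparison and 68% for both when the comparators share a trajectory. Apply the same comparator rule to H1b. As a secondary point, add a sentence on how alpha is handled between H1a and H1b.

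**Cost.** Wording in two sections. The primary outcome, the arms and the 309 recruits stay as they are, and no extra participants are needed. The downside is that the stated power for the joint claim becomes less favourable.
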